Original titel (dansk)

EDFI-Kohorten: Et kohortestudie om udviklingen af afføringsinkontinens og endetarmens lukkemuskelsfunktion, hos personer opereret for endetarmskræft.

Project title

The EDFI-Cohort: Determining early development of faecal incontinence and anorectal muscle function after curative surgery for rectal cancer.

Background

Patients who have been diagnosed with rectal cancer and treated with curative rectal surgery (low anterior resection (LAR)) have a high chance of survival (about 60% are alive after 5 years). [1] There is increasing focus on quality of life for these survivors. A stigmatized problem that more than a third of patients surgically treated for rectal cancer develop is faecal incontinence also known as the low anterior resection syndrome (LARS) [2-7], that has significant impact on quality of life. [8, 9] There is limited knowledge on why some patients develop major LARS. Some of the known exposures that increases the risk of developing major LARS are; age at surgery, gender, tumor height, pre-operative radiotherapy and surgical technique. The choice of surgical procedure is likely to play an important role in developing LARS, but has primarily been evaluated in smaller longitudinal studies with few patients (mean n ≈ 18 patients, range 3-100 patients). [10, 11]

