To guide the choice of surgical technique outcomes of mortality, adverse events and self-reported quality of life are important to report. As before mentioned LARS has significant impact on quality of life and is thus important to study. In order to evaluate the underlying mechanisms of LARS, and in the future provide effective treatments, it is central to evaluate the anorectal muscle function. Anorectal muscle function has been evaluated with anorectal manometry in patients who have been treated with low anterior resection at a median of 6 weeks (range 4-40 weeks) [12] and at a mean of 23 months (range 6-106 months) [13, 14] after surgery

Sexual dysfunction, urinary incontinence and fecal incontinence are present in patients with rectal cancer as long after surgery as 4 years, therefore it is important to determine if when these symptoms develop and how they are related to each other in patients treated for rectal cancer. [18] To our knowledge, no records exist on these relationships from prior to surgery to 2 years after low anterior resection. This type of information is central to the future design and conduct of expensive randomized trials.

Purpose

The primary purpose of the EDFI-Cohort study is to determine how several baseline variables (surgical technique, anorectal muscle function, faecal incontinence, urinary incontinence, sexual dysfunction, fatigue, physical activity, meaning in life and physical functioning) develop over time and predicts quality of life, and secondary how it predicts LARS-score in patients with rectal cancer from prior to surgery to 2 years after primary treatment.

Hypothesis

A priori, we determined the following major hypotheses for this study to be (with corresponding null hypotheses):

1. We expect to see poorer quality of life in patients with a higher LARS-score
2. Overall we expect to see poorer quality of life in patients with poor anorectal muscle function, faecal incontinence, urinary incontinence, sexual dysfunction, fatigue, low physical activity, low meaning in life and physical functioning.
3. We expect to a difference in quality of life and LARS-scores between surgical technique. We expect that PME will lead to fewer symptoms and TA-TME to worse symptoms compared with other techniques.
4. We expect to see no differences in mortality rate and adverse events between the different baseline variables.

Method

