Subjects for the EDFI-Cohort study will be recruited during 2019 and 2020 from Department of Surgery, Slagelse, and Zealand University Hospital, Køge. Subjects need to be diagnosed with rectal cancer and have received curative surgery (low anterior resection) with/without adjuvant (radiation/chemo) therapy. Subjects for this study are to meet the following inclusion criteria: Low anterior resection (e.g. not limited to total mesorectal excision (TME) or partial mesorectal excision (PME)), ability to communicate in Danish, adults (> 18 years of age), and American Society of Anaesthesiologists (ASA) score: I-IV. Exclusion criteria are: ASA score of: V-VI.

Prior to inclusion, subjects must provide written informed consent to participate in this study.

Subjects for the EDFI-Cohort study will be identified through surgical codes at Slagelse Hospital and Zealand University Hospital, Køge, Denmark. Eligible subjects will primarily be invited to participate in this study prior to discharge with oral and written information, provided in person by a health professional from the research group. Alternatively eligible subjects will be sent a letter after discharge. The letter and written information contain information on the study, the right to say no to the study, the right to 24 hours reflection time and the right to bring next of kin or another person of the subject's choice with him/her to the inclusion meeting. Potential subjects that are only invited by letter are asked to contact the research group for further information. A second letter will be sent to potential subjects whom have not contacted the research group within two weeks, and 2-3 weeks after the second letter has been sent, subjects will be contacted once by phone. Verbal and written information will be provided by a health professional from the research group at a meeting in an undisturbed examination room at Slagelse Hospital or Zealand University Hospital, Køge, Denmark.

Sample size:

The cohort will recruit all eligible patients from summer 2019 to April 2020. In this time period we estimate to recruit 70 patients to the EDFI cohort. A total of 86 patients were surgically treated for rectum cancer in 2017 at Slagelse Hospital and Zealand University Hospital, Køge.

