Digital examination of anorectal muscle function is an easy-to-use and cheap assessment tool readily available in a clinical setting. When using the Digital Rectal Examination Scoring System (DRESS) that ranges 0-5 (lowest to highest), the digital examination showed very high agreement with manometry pressures (Spearman rank correlation coefficients 0.81-0.82). [34] Digital examination involves inserting a finger in the anal canal.

High-Resolution AnoRectal Manometry (HR-ARM) is considered state of art in measuring anorectal muscle function and has shown to have moderate to high reliability in adults with or without faecal incontinence, with intra-individual correlations (ICC) for resting pressure (ICC 0.60-0.91) [35] [36] [16], squeezing pressure (ICC 0.49-0.95) [35] [36] [16] and rectal perception (ICC 0.75-0.92) [36] [16]. HR-ARM involves a narrow catheter being inserted in the anal canal that measures pressure with strain gauges several times throughout the anal canal. Rectal perception is measured by inflating a balloon in the rectal canal.

The Six-Minute Walk test (6MWT) is a widely used measure of submaximal exercise capacity in populations with and without pathology. [37] The 6MWT has shown to be correlated to maximum exercise capacity ($r=0.67$) and to perceived physical function (EORTC QLQ-C30 physical function subscale) ($r=0.55$) in cancer patients. [38] A systematic review has recommended that a minimal clinically important difference of ≥ 30.5 m for the 6MWT can be considered clinically meaningful for patients with a variety of pathology. [39] 6MWT involves the patient walking as far as possible in 6 minutes indoor.

Table 1: Full list of outcomes.

Patient records at hospital	Items that is obtained	Time point
Descriptive information:	Age at surgery (years) Time of surgery (weeks) Gender (male/female) Tumor height (cm from anal verge) Tumor stage (UICC) Involvement of lymph nodes (N stage) Additional radiotherapy/chemotherapy Surgical technique Anastomosis ASA grade (I-IV) Time with temporary stoma Manometric examination (if available) Digital examination (if available) Six-Minute Walk test (if available)	At identification of relevant patients
Adverse events from surgery	Hospitalisation 30 days after surgery Surgical complications	30 days after surgery
Mortality (and at the National Patient Registry)	Is the subject deceased?	If no answer is obtained through questionnaires or no show at clinical examination.

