Statistical analysis

We plan to analyze the EDFI-Cohort study as repeated measures with both simple and multiple linear regression models for the continuous data. We plan to adjust for the following known confounders: patient characteristics: age at surgery, gender, tumor height, tumor stages and variables related to treatment: surgical complications (e.g. nerve damage, sphincter rupture), additional radiotherapy/chemotherapy, time with stoma.

Patient involvement

Prior to planning of the EDFI-Cohort study, we have performed a single case-study (spring 2016) on examination procedure, questionnaires and pelvic floor muscle rehabilitation. This case provided us with valuable information on testing and possible evaluation of treatment effect. In the winter of 2017-18, we

interviewed subjects on their perspective on this study design and examination load. In the same time-period, we did pilot testing on the clinical examinations.

Research ethics

Examinations included in this study are all associated with very few, if any, adverse events, except from the mild discomfort related to the clinical anorectal examination itself. Subjects included in this study will receive four examinations, whereas care as usual at Slagelse and Køge Hospital usually include one examination/contact to the local LARS clinic with no anorectal examination. This, included subjects are more closely monitored and, if need be, might receive relevant treatment earlier compared to care as usual patients.

Future implications

Results from the EDFI-Cohort study will help guide the design of randomized controlled trials on treatments of faecal incontinence in subjects who have been surgically treated for rectal cancer. With emphasis on establishing the role of anorectal muscle function in the development of faecal incontinence.

Applicability of registrations and approvals

A prior version of the EDFI-Cohort study protocol has been approved by the regional research ethics committee of Region Zealand and The Data Protection Agency journal number: REG-130-2017. This project adhere to the General Data Protection Regulation and Data Protection Act. The regional research ethics committee and data protection agency will need to approve the new version of the study protocol prior to project start. Finally, the project will, prior to start, be registered at ClinicalTrials.gov. This study is part of the patient compensation scheme (patienterstatningsordningen).

Study economy

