This study is partially funded. Funding has so far come from the local research fund of NSR hospitals (DKK 968,000) and The Association of Danish Physiotherapists (DKK 82,000). The Department of Physiotherapy and Occupational Therapy at Slagelse Hospital provides access to facilities and offices. None of the funding agencies have any influence on study design or reporting of data. Further funding will be applied for from public and private foundations.

To reduce unnecessary inconvenience for subjects, we have planned the study test sessions on same days as subjects are to meet in the LARS outpatient clinics.

Dissemination of study results:

The EDFI-Cohort study is expected to be presented at several conferences for health professionals and the public and to provide 4 international peer-reviewed scientific papers on the findings whether they are positive, negative or inconclusive. All reporting of the EDFI-Cohort study will comply with the STROBE-guidelines [40, 41].

The first publication (paper 1) will report on associations between quality of life and LARS-score, adjusted for baseline variables (surgical technique, anorectal muscle function, faecal incontinence, urinary incontinence, sexual dysfunction, fatigue, physical activity, meaning in life and physical functioning) from prior to curative surgery until 12 weeks after surgery.

The second publication (paper 2) will report on the development of quality of life and LARS-score, stratified based on choice of surgical technique prior to curative surgery until 6 months after surgery.

The third publication (paper 3) will report on associations between quality of life and LARS-score, adjusted for baseline variables (surgical technique, anorectal muscle function, faecal incontinence, urinary incontinence, sexual dysfunction, fatigue, physical activity, meaning in life and physical functioning) from prior to curative surgery until 2 years after surgery.

The fourth publication (paper 4) will report on mortality rate and adverse events adjusted for baseline variables (surgical technique, anorectal muscle function, faecal incontinence, urinary incontinence, sexual dysfunction, fatigue, physical activity, meaning in life and physical functioning) from prior to curative surgery until 2 years after surgery.

References

1. Annual report 2017, in *Danish Colorectal Cancer Group*, D.C.C. Group, Editor. 2017, The Danish Clinical Registries and Danish Multidisciplinary Cancer Groups.

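### The single list of confounders includes surgical complications and time with stoma, which cannot confound the comparison of surgical techniques and may absorb part of the technique effect

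*Protocol*

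**What the plan says.** The Statistical analysis section plans simple and multiple linear regression on repeated measures. It names one set of known confounders without tying any of them to a particular exposure. The first part covers patient characteristics: age at surgery, gender, tumor height and tumor stages. The second part is "variables related to treatment: surgical complications (e.g. nerve damage, sphincter rupture), additional radiotherapy/chemotherapy, time with stoma".

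Other sections bear on this list:

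- **Hypothesis 3** makes surgical technique an exposure, in causal and directional terms: "We expect that PME will lead to fewer symptoms and TA-TME to worse symptoms compared with other techniques". The Sample size section bases both power statements on groups with different techniques, or with high or low anorectal muscle function.
- **Table 1** places complications under adverse events from surgery, at 30 days: "Hospitalisation 30 days after surgery Surgical complications". It lists "Time with temporary stoma" among the descriptive information from patient records.
- **Hypothesis 4** treats adverse events as an outcome: "We expect to see no differences in mortality rate and adverse events between the different baseline variables". Under Dissemination of study results, paper 4 does the same, and technique is among its baseline variables.

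**The concern.** A confounder of the technique comparison has to be, or stand in for, a common cause of the technique chosen and the later outcome. Nerve damage or sphincter rupture happens once the technique is already in use. The length of time with a stoma is settled later still. If the list is followed as written, the adjusted technique coefficient estimates only what does not pass through these variables. Hypothesis 3 is about the whole difference: a technique that led to worse symptoms by injuring nerves or the sphincter would have that part of its effect adjusted away.

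The simple model keeps that part but adjusts for nothing, so groups that differ in tumor height or stage are compared as they stand. Neither planned model gives a technique comparison adjusted only for what precedes the operation.

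**Working it through.** The protocol gives no figure on this point, so there is none to reproduce. The check has three steps.

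**1. Timing of each listed variable relative to technique**

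| Variable | When it is fixed | Possible common cause of technique and outcome? |
|---|---|---|
| Age, gender, tumor height, tumor stage | Before the operation | Yes |
| Additional radiotherapy/chemotherapy | Before or after; not separated | Only the part given before |
| Surgical complications | During or after the operation | No |
| Time with stoma | Accrues after the operation | No |

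The protocol therefore uses surgical adverse events in two roles: as an outcome compared across variables that include technique (hypothesis 4, paper 4), and as a confounder in the regressions.

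**2. What adjustment removes**

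In linear regression with otherwise identical covariates:

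technique coefficient without complications − technique coefficient with complications = a × b

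Here a is the adjusted difference in complication risk between techniques, and b is the coefficient of a complication in the outcome model. The protocol gives neither, so both are assumed:

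- a = 0, 5, 10 or 20 percentage points.
- b = 10 to 22 points for quality of life (10 is the protocol's target difference, 22 its SD).
- b = 6 to 12 points for LARS-score (6 is the target difference, 12 the SD).

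| a | Quality of life, a × 10 to a × 22 | LARS-score, a × 6 to a × 12 |
|---|---|---|
| 0 | 0 | 0 |
| 0.05 | 0.5 to 1.1 | 0.3 to 0.6 |
| 0.10 | 1.0 to 2.2 | 0.6 to 1.2 |
| 0.20 | 2.0 to 4.4 | 1.2 to 2.4 |

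The row a = 0 is the case in which hypothesis 4 is true.

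For scale, the Sample size section gives 7-12 points as the minimal important difference for quality of life. If the 70 patients split 35/35 (assumed), the standard error of a two-group difference at one time point is 22 × √(2/35) = 5.26 for quality of life and 12 × √(2/35) = 2.87 for LARS-score. Every entry in the table is below one such standard error. Repeated measures or more than two technique groups would change these standard errors.

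The same identity applies to stoma time, with a as the difference in mean duration. The protocol gives nothing from which to set a or b there.

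**3. Illustration by simulation**

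This used 400,000 simulated records with an assumed complication risk of 10% versus 30% and an assumed total technique effect of −10 points. The complication effect is set to share × (−10) / 0.20.

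| Share acting through complications | Complication effect | Coefficient without complications | Coefficient with complications |
|---|---|---|---|
| 0% | 0 | −9.97 | −9.96 |
| 10% | −5 | −9.97 | −8.98 |
| 25% | −12.5 | −9.89 | −7.46 |
| 50% | −25 | −9.88 | −4.88 |

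The model without complications recovers the total effect, and the adjusted model loses the mediated share. This shows the mechanism and says nothing about the actual share in this cohort.

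**The case against.** **The list is general, and the purpose speaks of prediction.** The Statistical analysis section never says that every item enters the technique model. In a purely predictive model, post-operative covariates are not an error. Detailed covariate sets are also often left to a SAP, which is not among the documents reviewed. These points limit the scope of the concern but do not remove it. The section calls the variables confounders, names no exception, and hypothesis 3 is worded causally. The point is to correct a stated rule, not to supply missing detail.

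**The simple model already gives an estimate free of these variables.** It does, but without control for tumor height and stage, so this mitigates the problem without resolving it.

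**Hypothesis 4 expects no difference in adverse events.** If that is true, nothing is lost through complications. It is still a hypothesis to be tested, and it does not cover stoma time.

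A reader might also infer more than the protocol supports:

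- *That stoma time is a mediator.* No section says that it differs by technique. If it does not, adjusting for it removes no technique effect by this route.
- *That the Background contradicts the list.* It names "known exposures that increases the risk of developing major LARS are; age at surgery, gender, tumor height, pre-operative radiotherapy and surgical technique", without complications or stoma time. But it introduces these as only some of the known exposures, it concerns major LARS rather than quality of life, and it also omits tumor stage, which belongs in the technique model. It is no evidence either way.
- *That paper 2 will use this adjustment.* It is described only as reporting "development of quality of life and LARS-score, stratified based on choice of surgical technique", with no adjustment set.
- *That the technique effect will be underestimated.* That requires the direct and mediated parts to share a sign. If they differ in sign, the adjusted coefficient can be too large.

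**Conclusion.** The point holds for technique as the exposure in hypothesis 3. Surgical complications are wrongly labelled as confounders of that comparison, and adjusting for them removes whatever part of the difference acts through them. Stoma time cannot be a common cause either, but the harm from adjusting for it is conditional on a difference between techniques that the protocol does not describe.

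The direction and size of the bias cannot be derived from the protocol, and it may be zero. The ranges of 0 to 4.4 quality-of-life points and 0 to 2.4 LARS points rest entirely on assumed risk differences and complication effects. No large bias has been shown. The case for the change is that the stated set does not answer the question hypothesis 3 asks and is cheap to correct. The change should be made, but the study does not stand or fall on it.

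The point does not extend to other exposures. Where LARS-score or anorectal muscle function is related to quality of life, complications and stoma time can be legitimate confounders.

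**What to change.** In the Statistical analysis section, state a separate adjustment set for surgical technique (hypothesis 3):

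- **Main adjusted model:** age at surgery, gender, tumor height, tumor stage, and radiotherapy/chemotherapy given before the operation.
- **Secondary model:** the same set plus surgical complications, time with stoma and post-operative therapy. Report it as a direct-effect analysis, noting that this reading also assumes no unmeasured common cause of the added variables and the outcome.
- **Other exposures**, such as LARS-score or anorectal muscle function: the full list may stay.

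The main model needs therapy to be recorded by timing, because the present list speaks only of additional therapy while the Method section describes patients who "have received curative surgery (low anterior resection) with/without adjuvant (radiation/chemo) therapy".

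The cost is two or three sentences and one extra secondary model. It uses patient-record data already planned and adds no patient contact.

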The minimal clinically important difference on the EORTC QLQ-C30 subscale Global Health Status is considered to be 7-12 points for a variety of cancer types (rectal cancer not studied). [19-22] Thus, with the estimated recruitment flow; we will have a power of 0.98 for a two-sample pooled t-test of a normal mean difference with two-sided significance level of 0.05 ($p \leq 0.05$), assuming a common SD of 22 EORTS QLQ-C30 points to detect a mean difference of 10 points between groups with different surgical techniques or with high or low anorectal muscle function (primary study purpose 1).

Additionally, we will have a power of 0.99 for a two-sample pooled t-test of a normal mean difference with two-sided significance level of 0.05 ($p \leq 0.05$), assuming a common SD of 12 LARS points [3] to detect a mean difference of 6 LARS points between groups with different surgical techniques or with high or low anorectal muscle function (study purpose 2).

Whether or not we are able to reach sufficient numbers within the 1 year timeframe, recruitment will end in April 2020.

Outcomes:

Outcomes is to be obtained from patient records, self-reported questionnaires and objective measures. For full list of outcomes to be collected and time points, see table 1.

Patient records:

In order to identify and invite eligible subjects, information on diagnosis, type of surgery, admission and contact information will be collected from patient records and given to the research group, prior to acceptance to participate in the study. After acceptance to participate in this study the following descriptive information will be collected from patient records (including electronic patient journals): Age at surgery (years), time of surgery (weeks), type of surgery, surgical complications, gender (male/female), tumor height (cm from anal verge), tumor stage (UICC), involvement of lymph nodes (N stage), additional radiotherapy/chemotherapy, surgical technique, anastomosis, ASA grade (I-IV), time with temporary stoma, and if available data from pre-surgery manometric examination, digital examination, Six-Minute Walk test (6MWT) and mortality status. This information will be used to adequately describe patient characteristics, cancer treatment, surgical outcome and mortality status. Additionally the acceptance to participate in this study allows the research group and relevant control agency direct access to collect information on health status in relation to quality control.

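### Table 1 collects stoma time and additional therapy too early to capture what the adjustment needs, and the parts that arise after surgery are not baseline confounders of the technique comparison

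*Protocol*

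**What the plan says.** **Adjustment.** The Statistical analysis section plans repeated-measures regression models. Among the treatment variables that it lists as known confounders are "additional radiotherapy/chemotherapy, time with stoma".

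**Timing in Table 1.** Both items stand in the descriptive row of the patient-record part of Table 1. That row includes "Additional radiotherapy/chemotherapy Surgical technique Anastomosis" and then "ASA grade (I-IV) Time with temporary stoma Manometric examination (if available". Its only time point is "At identification of relevant patients".

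**Timing in the text.** The Patient records section says: "After acceptance to participate in this study the following descriptive information will be collected from patient records". The list that follows contains both items and gives no date or end point. Before acceptance, that section allows only the information needed to find and invite patients.

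**When identification happens.** According to the Method section, patients are found through surgical codes, and "Eligible subjects will primarily be invited to participate in this study prior to discharge with oral and written information". A letter after discharge is the alternative.

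**Which therapy is meant.** The Background lists as known risk factors "age at surgery, gender, tumor height, pre-operative radiotherapy and surgical technique". The eligibility text in the Method section refers to "curative surgery (low anterior resection) with/without adjuvant (radiation/chemo) therapy". The Patient records section, Table 1 and the Statistical analysis section use the neutral word additional.

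**The concern.** A covariate is useful only if its value exists when it is collected. The length of time with a temporary stoma is known once the stoma has been closed, and therapy given after surgery is known once it has been given. A record read around discharge holds neither.

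There is a second problem, separate from timing. Hypothesis 3 predicts differences in quality of life and LARS-score between surgical techniques, and the Sample size section powers that comparison. Stoma duration and post-operative therapy come after the technique has been chosen. If the technique influences either of them, they lie on the path from technique to outcome, and conditioning on them takes out part of the effect that the hypothesis is about. Collecting the items later cures the first problem and not the second, so the schedule and the adjustment set both need attention.

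**Working it through.** No figure in the protocol depends on this point, so there is none to reproduce. The check sets the sections side by side and adds one illustration.

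**1. Can the items be complete at the scheduled time?**

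| Item | Known around discharge? | Later collection listed? |
|---|---|---|
| Pre-operative therapy | Yes | Not needed |
| Post-operative therapy | No | None |
| Total time with temporary stoma | No | None |

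Table 1 does give later time points to other record items: 30 days for adverse events from surgery, and non-response or a missed visit for mortality. It therefore separates later-occurring items elsewhere, but not these two.

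**2. Do Table 1 and the Patient records section agree?** No. Identification comes before acceptance, and the Patient records section holds these items back until after acceptance. Both cannot be followed. The later of the two times does not solve the problem by itself. Acceptance is mainly sought before discharge, and no end date is set. On the letter route, the last contact attempt comes 2 + 2 = 4 to 2 + 3 = 5 weeks after the first letter.

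**3. How much does the reading date matter?** The protocol gives no distribution of stoma time. As an assumption, let true stoma time T among patients with a stoma be uniform on 6 to 40 weeks, a span of 34 weeks. Let the recorded value be R = min(T, t), where t is the week at which the record is read. Then:

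- Share with the stoma still in place at t = (40 − t)/34 for t between 6 and 40. At 12 weeks this is 28/34 = 0.82, and at 26 weeks 14/34 = 0.41.
- With u = (t − 6)/34, the correlation of R with T is (u²/4 − u³/6) / √[(u³/3 − u⁴/4)/12].

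| Record read at | Share still censored | Correlation of recorded with true time |
|---|---|---|
| 1, 3 or 6 weeks | 1.00 | Undefined (every recorded value is the same) |
| 12 weeks | 0.82 | 0.60 |
| 26 weeks | 0.41 | 0.94 |
| 52 weeks | 0 | 1.00 |

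Under this assumption the covariate carries no information on duration if the record is read in the first six weeks, and full information if it is read at 52 weeks. A different distribution would move the intermediate rows. Whatever the distribution, a record read before any stoma is closed says nothing about duration. The loss depends on the reading date, which the protocol states in two conflicting ways.

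**4. Where do the items sit relative to the exposure?** The order is pre-operative therapy, then technique, then stoma time and post-operative therapy, with outcomes measured from week 3 to week 104. Only pre-operative therapy can be a baseline confounder of technique. In addition, a patient's total stoma time used as a covariate for a week 3 or week 6 outcome may be information from after that outcome.

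**The case against.** The best defence is that the Patient records section sets no end date, so nothing forbids completing these items from the records later. The same list contains surgical complications and mortality status, which Table 1 collects at other times, so the list is not a single early extraction. An item defined as a duration also suggests that someone will fill it in when it is known. This stands as far as it goes: the protocol does not rule out later completion. It does not require it either, and the one explicit time point, in Table 1, is too early.

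Several stronger readings are tempting, and the protocol does not support them.

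- **That radiotherapy and chemotherapy are pooled into one variable.** They share a slash-joined label in lists. No section says how they are coded, and coding may be left to the statistical analysis plan.
- **That the main radiotherapy risk factor is missed.** The Background names pre-operative radiotherapy, which is already in the record at identification.
- **That later therapy or stoma time will be entered as absent or zero.** No such coding rule appears.
- **That a number of misclassified patients can be stated.** The protocol gives no rate of post-operative therapy or of stoma closure, so any count out of the planned 70 would rest on an invented percentage.
- **That poor capture of these items leaves the technique comparison confounded.** If they arise after the technique is chosen, they should not be in that adjustment at all, so mismeasuring them is not a source of confounding there. Poor capture matters for the association between LARS-score and quality of life.

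**Conclusion.** The point holds in two parts. First, Table 1 and the Patient records section disagree on when these items are collected, and the Table 1 time cannot yield total stoma time or post-operative therapy, although the Statistical analysis section plans to adjust for stoma time and additional therapy. Second, stoma time and post-operative therapy are listed as known confounders without separating the analyses. For the technique comparison they are post-exposure variables, and adjusting for them can remove part of the technique effect.

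The size cannot be derived from the protocol. The 6-to-40-week illustration shows only that the loss ranges from complete to none according to the reading date. The first part assumes that Table 1 is followed as written. The second assumes that technique can affect stoma duration or later therapy, and the protocol gives no data on how strongly. This should be corrected, and early enough for the later extraction to be planned.

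**What to change.** 1. Reconcile Table 1 with the Patient records section, so that one collection time is stated for each item.
2. Extract the stoma closure date and any post-operative therapy, with dates, from the records at or after the end of the follow-up used in each analysis. The Dissemination section sets these ends at 12 weeks, 6 months and 2 years for papers 1 to 3.
3. Record pre-operative therapy as its own item at identification or acceptance, separate from post-operative therapy, and use these terms consistently in the Background, eligibility and analysis text.
4. Of these items, adjust technique comparisons for pre-operative therapy only.
5. In the analysis of LARS-score and quality of life, use stoma status and post-operative therapy as time-varying covariates, or report them as descriptors.

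The cost is one later record extraction, plus edits to Table 1 and the Statistical analysis section. A paper reported before the 2-year data are complete needs its extraction at its own cut-off. The Patient records section already covers collection of both items after acceptance, so no new patient contact is needed.
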